### **Holding Study Interventions:**

When study interventions are administered in combination and if the AE is considered immune-related, pembrolizumab monotherapy, coformulations, or IO combinations should be held according to recommended Dose Modification criteria.

If the toxicity does not resolve or the criteria for resuming treatment are not met, the participant must be discontinued from pembrolizumab monotherapy, coformulations, or IO combinations.

### **Restarting Study Interventions:**

Participants may restart pembrolizumab monotherapy, coformulations, or IO combinations as described below:

If the toxicities do resolve and conditions are aligned with what is defined in the Dose Modification and Toxicity Management Guidelines for irAEs, pembrolizumab monotherapy, coformulations, or IO combinations may be restarted at the discretion of the investigator.

Dose Modification and Toxicity Management Guidelines for irAEs associated with pembrolizumab monotherapy, coformulations, or IO combinations are provided in [Table 5](#).

Table 5 Dose Modification and Toxicity Management Guidelines for Immune-related Adverse Events Associated with Pembrolizumab Monotherapy, Coformulations or IO Combinations

General instructions:				
1. Severe and life-threatening irAEs should be treated with IV corticosteroids followed by oral steroids. Other immunosuppressive treatment should begin if the irAEs are not controlled by corticosteroids. 2. Pembrolizumab monotherapy, coformulations or IO combinations must be permanently discontinued if the irAE does not resolve or the corticosteroid dose is not $\leq 10$ mg/day within 12 weeks of the last treatment. 3. The corticosteroid taper should begin when the irAE is $\leq$ Grade 1 and continue at least 4 weeks. 4. If pembrolizumab monotherapy, coformulations or IO combinations have been withheld, treatment may resume after the irAE decreased to $\leq$ Grade 1 after corticosteroid taper.				
irAEs	Toxicity Grade (CTCAE v5.0)	Action With Pembrolizumab Monotherapy, Coformulations or IO Combinations	Corticosteroid and/or Other Therapies	Monitoring and Follow-up
Pneumonitis	Grade 2	Withhold	
 
Administer corticosteroids (initial dose of 1 to 2 mg/kg prednisone or equivalent) followed by taper
 
Add prophylactic antibiotics for opportunistic infections
 
	
 
Monitor participants for signs and symptoms of pneumonitis
 
Evaluate participants with suspected pneumonitis with radiographic imaging and initiate corticosteroid treatment
 

	Recurrent Grade 2, Grade 3 or 4	Permanently discontinue		
Diarrhea/ Colitis	Grade 2 or 3	Withhold	
 
Administer corticosteroids (initial dose of 1 to 2 mg/kg prednisone or equivalent) followed by taper
 
	
 
Monitor participants for signs and symptoms of enterocolitis (ie, diarrhea, abdominal pain, blood or mucus in stool with or without fever) and of bowel perforation (ie, peritoneal signs and ileus)
 
Participants with <math>\geq</math>Grade 2 diarrhea suspecting colitis should consider GI consultation and performing endoscopy to rule out colitis
 
Participants with diarrhea/colitis should be advised to drink liberal quantities of clear fluids. If sufficient oral fluid intake is not feasible, fluid and electrolytes should be substituted via IV infusion
 

	Recurrent Grade 3 or Grade 4	Permanently discontinue		

irAEs	Toxicity Grade (CTCAE v5.0)	Action With Pembrolizumab Monotherapy, Coformulations or IO Combinations	Corticosteroid and/or Other Therapies	Monitoring and Follow-up
AST or ALT Elevation or Increased Bilirubin	Grade 2 a	Withhold	
 
Administer corticosteroids (initial dose of 0.5 to 1 mg/kg prednisone or equivalent) followed by taper
 
	
 
Monitor with liver function tests (consider weekly or more frequently until liver enzyme value returned to baseline or is stable)
 

	Grade 3 b or 4 c	Permanently discontinue	
 
Administer corticosteroids (initial dose of 1 to 2 mg/kg prednisone or equivalent) followed by taper
 
	
T1DM or Hyperglycemia	New onset T1DM or Grade 3 or 4 hyperglycemia associated with evidence of $\beta$ -cell failure	Withhold d	
 
Initiate insulin replacement therapy for participants with T1DM
 
Administer antihyperglycemic in participants with hyperglycemia
 
	
 
Monitor participants for hyperglycemia or other signs and symptoms of diabetes
 

Hypophysitis	Grade 2	Withhold	
 
Administer corticosteroids and initiate hormonal replacements as clinically indicated
 
	
 
Monitor for signs and symptoms of hypophysitis (including hypopituitarism and adrenal insufficiency)
 

	Grade 3 or 4	Withhold or permanently discontinue d		
Hyperthyroidism	Grade 2	Continue	
 
Treat with nonselective beta-blockers (eg, propranolol) or thionamides as appropriate
 
	
 
Monitor for signs and symptoms of thyroid disorders
 

	Grade 3 or 4	Withhold or permanently discontinue d		
Hypothyroidism	Grade 2, 3 or 4	Continue	
 
Initiate thyroid replacement hormones (eg, levothyroxine or liothyronine) per standard of care
 
	
 
Monitor for signs and symptoms of thyroid disorders
 

irAEs	Toxicity Grade (CTCAE v5.0)	Action With Pembrolizumab Monotherapy, Coformulations or IO Combinations	Corticosteroid and/or Other Therapies	Monitoring and Follow-up
Nephritis: grading according to increased creatinine or acute kidney injury	Grade 2	Withhold	
 
Administer corticosteroids (prednisone 1 to 2 mg/kg or equivalent) followed by taper
 
	
 
Monitor changes of renal function
 

	Grade 3 or 4	Permanently discontinue		
Neurological Toxicities	Grade 2	Withhold	
 
Based on severity of AE administer corticosteroids
 
	
 
Ensure adequate evaluation to confirm etiology and/or exclude other causes
 

	Grade 3 or 4	Permanently discontinue		
Myocarditis	Asymptomatic cardiac enzyme elevation with clinical suspicion of myocarditis (which was previously myocarditis Grade 1 using CTCAE v4.0)	Withhold	
 
Based on severity of AE administer corticosteroids
 
	
 
Ensure adequate evaluation to confirm etiology and/or exclude other causes
 

	Grade 2, 3 or 4	Permanently discontinue		
Exfoliative Dermatologic Conditions	Suspected SJS, TEN, or DRESS	Withhold	
 
Based on severity of AE administer corticosteroids
 
	
 
Ensure adequate evaluation to confirm etiology or exclude other causes
 

	Confirmed SJS, TEN, or DRESS	Permanently discontinue		
All Other irAEs	Persistent Grade 2	Withhold	
 
Based on severity of AE administer corticosteroids
 
	
 
Ensure adequate evaluation to confirm etiology or exclude other causes
 

	Grade 3	Withhold or discontinue based on the event c		
	Recurrent Grade 3 or Grade 4	Permanently discontinue		

irAEs	Toxicity Grade (CTCAE v5.0)	Action With Pembrolizumab Monotherapy, Coformulations or IO Combinations	Corticosteroid and/or Other Therapies	Monitoring and Follow-up

AE(s)=adverse event(s); ALT= alanine aminotransferase; AST=aspartate aminotransferase; CTCAE=Common Terminology Criteria for Adverse Events; DRESS=Drug Rash with Eosinophilia and Systemic Symptom; GI=gastrointestinal; IO=immuno-oncology; ir=immune related; IV=intravenous; SJS=Stevens-Johnson Syndrome; T1DM=type 1 diabetes mellitus; TEN=Toxic Epidermal Necrolysis; ULN=upper limit of normal.
 
Note: Non-irAE will be managed as appropriate, following clinical practice recommendations.
 
a AST/ALT: >3.0 to 5.0 x ULN if baseline normal; >3.0 to 5.0 x baseline, if baseline abnormal; bilirubin:>1.5 to 3.0 x ULN if baseline normal; >1.5 to 3.0 x baseline if baseline abnormal
 
b AST/ALT: >5.0 to 20.0 x ULN, if baseline normal; >5.0 to 20.0 x baseline, if baseline abnormal; bilirubin:>3.0 to 10.0 x ULN if baseline normal; >3.0 to 10.0 x baseline if baseline abnormal
 
c AST/ALT: >20.0 x ULN, if baseline normal; >20.0 x baseline, if baseline abnormal; bilirubin: >10.0 x ULN if baseline normal; >10.0 x baseline if baseline abnormal
 
d The decision to withhold or permanently discontinue pembrolizumab monotherapy, coformulations or IO combinations is at the discretion of the investigator or treating physician. If control achieved or ≤ Grade 2, pembrolizumab monotherapy, coformulations or IO combinations may be resumed.
 
e Events that require discontinuation include, but are not limited to: encephalitis and other clinically important irAEs (eg, vasculitis and sclerosing cholangitis).
				

**Dose Modification and Toxicity Management of Infusion Reactions Related to MK-7684A or Pembrolizumab**

MK-7684A or pembrolizumab may cause severe or life-threatening infusion-reactions including severe hypersensitivity or anaphylaxis. Signs and symptoms usually develop during or shortly after drug infusion and generally resolve completely within 24 hours of completion of infusion. Dose modification and toxicity management guidelines on MK-7684A or pembrolizumab associated infusion reaction are provided [Table 6](#).

Table 6 MK-7684A or Pembrolizumab Infusion Reaction Dose Modification and Treatment Guidelines

NCI CTCAE Grade	Treatment	Premedication at Subsequent Dosing
Grade 1 Mild reaction; infusion interruption not indicated; intervention not indicated	Increase monitoring of vital signs as medically indicated until the participant is deemed medically stable in the opinion of the investigator	None
Grade 2 Requires therapy or infusion interruption but responds promptly to symptomatic treatment (eg, antihistamines, NSAIDs, narcotics, IV fluids); prophylactic medications indicated for ≤24 hrs	
Stop Infusion
 
Additional appropriate medical therapy may include but is not limited to:                      IV fluids                      Antihistamines                      NSAIDs                      Acetaminophen                      Narcotics
 
Increase monitoring of vital signs as medically indicated until the participant is deemed medically stable in the opinion of the investigator.
 
If symptoms resolve within 1 hour of stopping drug infusion, the infusion may be restarted at 50% of the original infusion rate (eg, from 100 mL/hr to 50 mL/hr). Otherwise dosing will be held until symptoms resolve and the participant should be premedicated for the next scheduled dose.
 
Participants who develop Grade 2 toxicity despite adequate premedication should be permanently discontinued from further study drug intervention.
	
Participant may be premedicated 1.5 h (±30 minutes) prior to infusion of study intervention with:
 
Diphenhydramine 50 mg PO (or equivalent dose of antihistamine).                      Acetaminophen 500-1000 mg PO (or equivalent dose of analgesic).

NCI CTCAE Grade	Treatment	Premedication at Subsequent Dosing
Grades 3 or 4 Grade 3: Prolonged (ie, not rapidly responsive to symptomatic medication and/or brief interruption of infusion); recurrence of symptoms following initial improvement; hospitalization indicated for other clinical sequelae (eg, renal impairment, pulmonary infiltrates) Grade 4: Life-threatening; pressor or ventilatory support indicated	Stop Infusion. Additional appropriate medical therapy may include but is not limited to: Epinephrine** IV fluids Antihistamines NSAIDs Acetaminophen Narcotics Oxygen Pressors Corticosteroids Increase monitoring of vital signs as medically indicated until the participant is deemed medically stable in the opinion of the investigator. Hospitalization may be indicated. **In cases of anaphylaxis, epinephrine should be used immediately. Participant is permanently discontinued from further study drug intervention.	No subsequent dosing
Appropriate resuscitation equipment should be available at the bedside and a physician readily available during the period of drug administration. For further information, please refer to the Common Terminology Criteria for Adverse Events v5.0 (CTCAE) at http://ctep.cancer.gov		

**Other Allowed Dose Interruption for MK-7684A or Pembrolizumab**

MK-7684A or pembrolizumab may be interrupted for situations other than treatment-related AEs such as medical or surgical events and/or unforeseen circumstances not related to study intervention. However, study intervention is to be restarted within 3 weeks of the originally scheduled dose and within 6 weeks of the previously administered dose, unless otherwise discussed with the Sponsor. The reason for study intervention interruption is to be documented in the participant's study record.

**6.6.2 Initial Treatment or First Course**

The initial treatment or first course of MK-7684A Q3W or pembrolizumab Q3W consists of 35 treatments (approximately 2 years). Note: The number of treatments is calculated starting with the first dose.

For participants who have attained a confirmed CR and have received at least 8 doses of MK-7684A or pembrolizumab, including at least 2 doses of MK-7684A or pembrolizumab beyond the initial CR confirmation date, treatment may be stopped.

These participants may be eligible for Second Course, as described in Section 6.6.3.

### **6.6.3 Second Course**

All participants who have SD, PR, or CR may be eligible for up to an additional 17 cycles of MK-7684A or pembrolizumab treatment based on original randomization assignment if there is BICR verification of radiographic disease progression by RECIST 1.1 after initial treatment or first course has been completed or stopped for confirmed CR, as specified in Section 6.6.2. This retreatment is the Second Course of this study.

Participants may enter the Second Course if all of the following criteria are met:

1. No new anticancer treatment was administered after the last dose of study intervention
2. The participant meets all of the inclusion criteria and none of the exclusion criteria
3. The study is ongoing

An objective response or disease progression that occurs during the Second Course will not be counted as an event for the primary analysis of either endpoint in this study.

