## 2 INTRODUCTION

MK-7684A is a coformulation of MK-7684 and pembrolizumab. MK-7684 is a humanized, antagonist mAb that binds to the immune checkpoint receptor, TIGIT, and blocks the interaction between TIGIT and its ligands. Pembrolizumab is a potent humanized IgG4 mAb with high specificity of binding to the PD-1 receptor, thus inhibiting its interaction with PD-L1 and PD-L2. The coformulation of MK-7684A is being developed as a cancer immunotherapeutic with the potential to be used to increase benefit to patients with metastatic NSCLC.

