#### 4.3.3 Maximum Dose Exposure for This Study

The maximum dose/exposure of MK-7684A allowed in this study is 200 mg MK-7684/200 mg pembrolizumab for up to 2 years (35 treatment cycles) of initial treatment (Section 6.6.2) and an additional 1 year (17 cycles) for Second Course (Section 6.6.3).

The maximum dose/exposure of pembrolizumab allowed in this study is 200 mg IV Q3W for up to 2 years (35 treatment cycles) of initial treatment (Section 6.6.2) and an additional 1 year (17 cycles) for Second Course (Section 6.6.3).

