### Prior/Concomitant Therapy

2. Has received prior systemic chemotherapy or other targeted or biological antineoplastic therapy for their metastatic NSCLC.

Note: Prior treatment with chemotherapy and/or radiation as part of neoadjuvant/adjuvant or chemoradiation therapy for nonmetastatic NSCLC is allowed as long as therapy was completed at least 6 months before the diagnosis of metastatic NSCLC.

Note: Participants must have recovered from all AEs due to previous therapies to Grade  $\leq 1$  or baseline. Participants with Grade  $\leq 2$  neuropathy may be eligible. Participants with endocrine-related AEs Grade  $\leq 2$  requiring treatment or hormone replacement may be eligible.

3. Has received prior therapy with an anti-PD-1, anti-PD-L1, or anti-PD-L2 agent or with an agent directed to another stimulatory or co-inhibitory T-cell receptor (eg, CTLA-4, OX-40, CD137).
4. Has received previous treatment with another agent targeting the TIGIT receptor pathway.
5. Has received radiotherapy within 2 weeks of start of study intervention. Participants must have recovered from all radiation-related toxicities, not require corticosteroids, and not have had radiation pneumonitis. A 1-week washout is permitted for palliative radiation ( $\leq 2$  weeks of radiotherapy) to non-CNS disease.
6. Has received a live or live-attenuated vaccine within 30 days prior to the first dose of study intervention. Administration of killed vaccines is allowed. Refer to Section 6.5 for information on COVID-19 vaccines.

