##### **8.11.5.2 Efficacy Follow-up Visits**

Participants who complete the protocol-required cycles of study intervention or who discontinue study intervention for a reason other than disease progression will begin Efficacy Follow-up and should be assessed every 12 weeks to monitor disease status. Every effort should be made to collect information regarding disease status until the start of new anticancer therapy, disease progression, death, end of study. Information regarding poststudy anticancer treatment will be collected if new treatment is initiated. Participants who completed all efficacy assessments and/or will not have further efficacy assessments must enter Survival Follow-up.

Participants who are eligible to receive retreatment with pembrolizumab or MK-7684A according to the criteria in Section 6.6.3 will move from the Efficacy Follow-up Phase to the Second Course Phase when they experience disease progression. Details are provided in the SoA (Section 1.3) for retreatment with pembrolizumab.

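### Do the Second Course entry criteria shut out every participant who could use them?

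*Combined protocol and SAP*

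**What the plan says.** Section 6.6.3 offers participants who completed the first course, or stopped it after a confirmed complete response, up to "an additional 17 cycles of MK-7684A or pembrolizumab treatment based on original randomization assignment" once central review has verified progression. Three conditions must hold. The first is that "No new anticancer treatment was administered after the last dose of study intervention", the second that "The participant meets all of the inclusion criteria and none of the exclusion criteria", and the third that the study is still running.

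The second condition sends the reader to Section 5.2. Exclusion criterion 2 there reads "Has received prior systemic chemotherapy or other targeted or biological antineoplastic therapy for their metastatic NSCLC". Exclusion criterion 3 begins "Has received prior therapy with an anti-PD-1, anti-PD-L1, or anti-PD-L2 agent". Section 2 describes the drug common to both arms: "Pembrolizumab is a potent humanized IgG4 mAb with high specificity of binding to the PD-1 receptor".

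Other sections treat retreatment as a working part of the design. Section 4.3.3 sets maximum exposure at 35 cycles plus "an additional 1 year (17 cycles) for Second Course". Section 8.11.5.2 says that eligible participants "will move from the Efficacy Follow-up Phase to the Second Course Phase when they experience disease progression".

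**The concern.** Put side by side, the entry condition and the two exclusion criteria seem to cancel the Second Course. Nobody can be a candidate without having had pembrolizumab, alone or within MK-7684A, for metastatic NSCLC, and that history is what exclusion criteria 2 and 3 describe. If the text binds literally, nobody may be retreated, and anyone who was retreated entered against the protocol.

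Three features strengthen the worry. The protocol writes exemptions where it wants them: exclusion criterion 1 spares the NSCLC under study, and exclusion criterion 4 speaks of another anti-TIGIT agent, which can be read as sparing study drug. Exclusion criteria 2 and 3 have nothing similar for pembrolizumab. Section 5 forbids waivers of enrollment criteria. And the eligibility row of Table 2, the Second Course schedule, carries no note on which criteria apply.

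At stake would be inconsistent site decisions on who is retreated, a set of apparent protocol deviations, and possible doubt about analyses that involve retreated participants.

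**Working it through.** No formula applies, so the check compares the passages.

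**1. Who can be a candidate.** Sections 4.1, 6.6.2 and 6.6.3 limit the Second Course to participants who received 35 cycles, or who stopped for a confirmed complete response after at least 8 doses. All of them have had pembrolizumab.

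**2. The literal reading.** If first-course study drug counts as prior therapy, every candidate meets exclusion criteria 2 and 3, and no one can satisfy entry condition 2. The 17 further cycles in Sections 4.3.3 and 6.6.3 then serve no purpose. This shows that the reading is untenable; it does not measure harm.

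**3. The reading in context.** Entry condition 1 restricts only treatment given after the last study dose, which makes sense only if the study treatment itself is acceptable. Retreatment follows the randomized assignment, which presupposes earlier study drug. Section 8.11.5.2 describes the move into retreatment as routine.

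**4. What *prior* can mean.** Section 5.2 lists reasons to keep an individual out of the study. Exclusion criteria 5, 6 and 7, next to those at issue, count back from the start or first dose of study intervention. Section 4.1 describes enrolled participants as previously untreated for Stage IV disease, and Section 8.1.5.1 counts prior medication back from the start of the study. With that anchor, exclusion criteria 2 and 3 concern a history fixed at study entry. A participant who did not meet them then does not meet them at retreatment. Inclusion criterion 6 works in the same way: an ECOG status of 0 or 1 recorded before randomization remains true later, and Table 2 asks separately for a fresh ECOG assessment at Second Course Cycle 1.

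**5. Whether any analysis depends on the answer.**

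| Analysis | Plan | Depends on the validity of retreatment entry? |
|---|---|---|
| OS | Randomization to death, all randomized participants (9.4.1, 9.5.1) | No |
| PFS, OR, DOR | Only events and responses before the Second Course (9.6.1) | No; centrally verified progression must already have occurred before entry |
| Primary safety | Only events before the Second Course (9.6.2) | No |
| Analysis populations | ITT, APaT, PRO FAS (9.5.1 to 9.5.3) | No; none removes a participant for a deviation |
| Exposure | Cycles actually received (9.12) | No |

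**6. Whether the text still operates.** The Amendment 06 list at the head of Section 6 supersedes earlier instructions and retains the old content for historical reference. It stops central reading of scans, although Sections 6.6.3 and 8.2.1.4 require central verification of progression before entry. It also takes participants off study after the end-of-treatment visit and any required safety follow-up, which closes the route through Efficacy Follow-up.

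**The case for a change.** The strongest reply is that eligibility text should mean what it says. A clear intent is still an inferred one, and a site or auditor working word for word could record each retreatment as a deviation. The protocol shows elsewhere that it can write an exemption in a few words, and the eligibility row of Table 2 gives no help.

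Much of this stands. No visible passage exempts first-course treatment, so on one available reading the sections conflict. Deviation reporting is the one place where the classification might surface: Section 9.2 has deviations identified before unblinding, and Section 9.11 has departures from directed administration reported. That would affect a listing, not an estimate.

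The check also has limits. The Second Course schema (Figure 2) cannot be read in the available copy, and Table 2 ends there without the footer that Table 1 has. Parts of Section 9.6.2 and all of Section 9.10 are redacted, and the supplemental SAP is a separate document. The conclusion therefore covers the visible analyses only.

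The reply does not show that anyone was misled. Nothing in the documents suggests that a site refused retreatment on this ground, and the surrounding text points one way.

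**Conclusion.** This is a clerical gap, and correcting it now would gain nothing. Entry condition 2 borrows the full eligibility list without saying how first-course study drug is counted, and on a literal reading it contradicts the retreatment that the same section offers. A reader can resolve it from Section 6.6.3 itself, from the exposure limit in Section 4.3.3 and from the pathway in Section 8.11.5.2.

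None of the visible efficacy or primary safety analyses changes under either reading, and nothing in the argument touches OS, the sample size or the error rate. The number of participants who entered the Second Course is not given, but those analyses do not depend on it.

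The conclusion rests on two assumptions: that the redacted parts and the supplemental SAP contain no analysis that selects on valid Second Course entry, and that Amendment 06 operates as written. If the section were ever reissued for another reason, Sections 5.2 and 6.6.3 and the eligibility row of Table 2 would have to be reconciled, and which criteria apply at re-entry is for the sponsor to decide. That possibility does not justify an amendment, a statement in the study report or a re-analysis now.
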